6.2 Dose Modifications for Non-Hematological Toxicity

- 6.2.1 If a patient experiences non-hematological dose-limiting toxicity as defined in [Section 5.5.1](#), the treatment will be held. When the toxicity resolves to meet eligibility parameters or baseline within 14 days of drug discontinuation, the patient may resume treatment at the next lower dose level. For patients enrolled at Dose Level -1 (see [Section 5.3.1](#)), the dose should be reduced to $1.6 \text{ mg}/\text{m}^2$. Doses reduced for toxicity will not be re-escalated, even if there is minimal or no toxicity with the reduced dose.
- 6.2.2 If toxicity does not resolve to meet eligibility or baseline parameters within 14 days of drug discontinuation, the patient must be removed from protocol therapy.
- 6.2.3 If the same dose-limiting toxicity recurs in a patient who has resumed treatment at the reduced dose level, the patient must be removed from protocol therapy.

7.0 SUPPORTIVE CARE AND OTHER CONCOMITANT THERAPY

7.1 Concurrent Anticancer Therapy

Concurrent cancer therapy, including chemotherapy, radiation therapy, immunotherapy, or biologic therapy may NOT be administered to patients receiving study drug. If these treatments are administered, the patient will be removed from protocol therapy.

7.2 Investigational Agents

No other investigational agents may be given while the patient is on study.

7.3 Supportive Care

Appropriate antibiotics, blood products, antiemetics, fluids, electrolytes and general supportive care are to be used as necessary. Careful monitoring of electrolytes for hypophosphatemia and other electrolyte imbalances during treatment with entinostat is recommended and electrolyte supplementation may be warranted. See COG Supportive Care Guidelines at <https://childrensoncologygroup.org/index.php/cog-supportive-care-guidelines>. See [Section 4.2.2](#) for drugs that should not be used concomitantly with entinostat.

7.4 Growth Factors

Growth factors that support platelet or white cell number or function are not allowed.

7.5 Concomitant Medications

Concurrent therapy with valproic acid is not allowed for patients receiving study drug.

8.0 EVALUATIONS/MATERIAL AND DATA TO BE ACCESSIONED

8.1 Required Clinical, Laboratory and Disease Evaluation

All clinical and laboratory studies to determine eligibility must be performed within 7 days prior to enrollment unless otherwise indicated. Laboratory values used to assess eligibility (see [Section 4.0](#)) must be no older than seven (7) days at the start of therapy. Laboratory tests need **not** be repeated if therapy starts **within** seven (7) days of obtaining labs to assess eligibility. If a post-enrollment lab value is outside the limits of eligibility, or laboratory values are older than 7 days, then the following laboratory evaluations must be re-checked within 48 hours prior to initiating therapy: CBC with differential, bilirubin, ALT (SGPT) and serum creatinine. If the recheck is outside the limits of eligibility, the patient may not receive protocol therapy and will be considered off protocol therapy. Imaging studies must be obtained within 14 days prior to start of protocol therapy (repeat the tumor imaging if necessary).

STUDIES TO BE OBTAINED	Pre-Study	During Cycle 1	Prior to Subsequent Cycles[^]
History	X	Weekly	X
Physical Exam with vital signs	X	Weekly	X
Height, weight, BSA	X		X
Performance Status	X		
CBC, differential, platelets	X	Twice Weekly	Weekly ³
Pharmacokinetics ¹	X	X	X
Urinalysis	X		
Electrolytes including Ca ²⁺ , PO ₄ ³⁻ , Mg ²⁺ ; glucose	X	Weekly	X
Creatinine, ALT, bilirubin	X	Weekly	X
Albumin	X		X
Tumor Disease Evaluation	X	End of Cycle 1	Every other cycle x 2 then q 3 cycles ⁴
Pharmacodynamics Studies (H3 and H4 Histone Acetylation in PBMCs) ⁶	X	X ⁷	
Pregnancy Test ²	X		
Patient Diary ⁵		Weekly	X

[^] Studies may be obtained within 72 hours prior to the start of the subsequent cycle.

¹ See [Section 8.3](#) for timing of PK studies.

² Women of childbearing potential require a negative pregnancy test prior to starting treatment; sexually active patients must use an acceptable method of birth control. Abstinence is an acceptable method of birth control. Patients of reproductive potential must use secure methods of contraception during treatment and for 3 additional months after the end of treatment. Those who become pregnant while on treatment with entinostat must discontinue immediately and consult their treating physician.

³ If patients develop Grade 4 neutropenia or Grade 4 thrombocytopenia then CBCs should be checked every 3 to 4 days until recovery to Grade 3.

⁴ Tumor Disease Evaluation should be obtained on the next consecutive cycle after initial documentation of either a PR or CR. Subsequent scans may restart 2 cycles after the confirmatory scan. Please note that for solid tumor patients, if the institutional investigator determines that the patient has progressed based on clinical or laboratory evidence, he/she may opt not to confirm this finding radiographically.

⁵ Patient diary (see [Appendix V](#)) should be reviewed after completion of each treatment cycle and uploaded into RAVE. During Cycle 1, patient diary should be reviewed weekly and uploaded into RAVE.

⁶ These blood draws will only occur in patients who consent to this optional component of the study.

[figure not shown]
⁷ See [Section 8.4](#) for timing of the pharmacodynamics studies.

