4.1 Inclusion Criteria

- 4.1.1 Age: Patients must be \geq than 12 months and \leq 21 years of age at the time of study enrollment.
- 4.1.2 Patients must have a BSA of $\geq 1.17 \text{ m}^2$ at time of study enrollment.
- 4.1.3 Patients must be able to swallow intact tablets.
- 4.1.4 Diagnosis: Patients with recurrent or refractory solid tumors, including CNS tumors or lymphoma, are eligible. Patients must have had histologic verification of malignancy at original diagnosis or relapse except in patients with intrinsic brain stem tumors, optic pathway gliomas, or patients with pineal tumors and elevations of CSF or serum tumor markers including alpha-fetoprotein or beta-HCG.
- 4.1.5 Disease Status:
Patients must have either measurable or evaluable disease (see Sections [12.2](#) and [12.3](#) for definitions).
- 4.1.6 Therapeutic Options: Patient's current disease state must be one for which there is no known curative therapy or therapy proven to prolong survival with an acceptable quality of life.
- 4.1.7 Performance Level: Karnofsky $\geq 50\%$ for patients > 16 years of age and Lansky ≥ 50 for patients ≤ 16 years of age (See [Appendix I](#)). Note: Neurologic deficits in patients with CNS tumors must have been relatively stable for at least 7 days prior to study enrollment. Patients who are unable to walk because of paralysis, but who are up in a wheelchair, will be considered ambulatory for the purpose of assessing the performance score.
- 4.1.8 Prior Therapy
Patients must have fully recovered from the acute toxic effects of all prior anti-cancer therapy and must meet the following minimum duration from prior anti-cancer directed therapy prior to enrollment. If after the required timeframe, the defined eligibility criteria are met, e.g. blood count criteria, the patient is considered to have recovered adequately.
- a. Cytotoxic chemotherapy or other anti-cancer agents known to be myelosuppressive. See DVL homepage for commercial and Phase I investigational agent classifications. For agents not listed, the duration

of this interval must be discussed with the study chair and the study-assigned Research Coordinator prior to enrollment.

i. *Solid Tumor Patients*: ≥ 21 days after the last dose of cytotoxic or myelosuppressive chemotherapy (42 days if prior nitrosourea).

ii. *Lymphoma Patients*:

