4.1.9 Organ Function Requirements

4.1.9.1 Adequate Bone Marrow Function Defined as:

- a. For patients with solid tumors, including lymphoma, without known bone marrow involvement:
 - Peripheral absolute neutrophil count (ANC) $\geq 1000/\text{mm}^3$
 - Platelet count $\geq 100,000/\text{mm}^3$ (transfusion independent, defined as not receiving platelet transfusions for at least 7 days prior to enrollment)
 - Hemoglobin ≥ 8.0 g/dl, with or without transfusion
- b. Patients with known bone marrow metastatic disease will not be eligible.

4.1.9.2 Adequate Renal Function Defined as:

- Creatinine clearance or radioisotope GFR $\geq 70\text{ml}/\text{min}/1.73 \text{ m}^2$ or
- A serum creatinine based on age/gender as follows:

Age	Maximum Serum Creatinine (mg/dL)	
	Male	Female
1 to < 2 years	0.6	0.6

2 to < 6 years	0.8	0.8
6 to < 10 years	1	1
10 to < 13 years	1.2	1.2
13 to < 16 years	1.5	1.4
≥ 16 years	1.7	1.4

The threshold creatinine values in this Table were derived from the Schwartz formula for estimating GFR³³ utilizing child length and stature data published by the CDC.

4.1.9.3 Adequate Liver Function Defined as:

- Bilirubin (sum of conjugated + unconjugated) ≤ 1.5 x upper limit of normal (ULN) for age
- SGPT (ALT) ≤ 3 × ULN = 135 U/l. For the purpose of this study, the ULN for SGPT is 45 U/l.
- Serum albumin ≥ 2 g/dl.

4.1.10 Informed Consent: All patients and/or their parents or legally authorized representatives must sign a written informed consent. Assent, when appropriate, will be obtained according to institutional guidelines.

4.2 **Exclusion Criteria**

4.2.1 Pregnancy or Breast-Feeding:

Pregnant or breast-feeding women will not be entered on this study due to risks of fetal and teratogenic adverse events as seen in animal studies. Pregnancy tests must be obtained in girls who are post-menarchal. Males or females of reproductive potential may not participate unless they have agreed to use an effective contraceptive method both during and for 3 months after participation in this study. Abstinence is an acceptable method of contraception. Those who become pregnant while on treatment with entinostat must discontinue immediately and consult their treating physician.

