5.0 TREATMENT PROGRAM

5.1 Overview of Treatment Plan

		Entinostat oral	Action
Week 1	Day 1	X	
Week 2	Day 8	X	
Week 3	Day 15	X	
Week 4	Day 22	X	
End of Cycle	Day 28		Evaluation

Entinostat will be administered orally on Days 1, 8, 15, and 22 of a 28-day cycle. Patients may continue to receive entinostat for up to 5 years.

Drug doses should be adjusted based on the BSA calculated from height and weight measured within 7 days prior to the beginning of each cycle. If a patient vomits within 30 minutes after the dose of entinostat is administered, that dose may be repeated. If vomiting occurs greater than 30 minutes after the administered dose, the dose will not be repeated. If a patient misses an entinostat dose and less than 12 hours have passed since the scheduled dosing time, that dose should be taken immediately. If a patient misses an entinostat dose and more than 12 hours have passed since the scheduled dosing time, this dose will be skipped. If a patient accidentally takes an extra dose during a day, the next scheduled dose of entinostat will be skipped.

The patient/family will be asked to complete a Patient Medication Diary (see [Appendix V](#)).

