5.2 Criteria for Starting Subsequent Cycles

A cycle may be repeated every 28 days if the patient has at least stable disease and has again met laboratory parameters as defined in the eligibility section, [Section 4.0. Section 4.0](#)

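### A pregnancy test is required only before treatment starts; none is scheduled before later cycles or explicitly required when a girl reaches menarche on study

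*Combined protocol and SAP*

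**What the plan says.** The 8.1 table has three timing columns: pre-study, during Cycle 1, and prior to subsequent cycles. The pregnancy-test row is marked in the first and blank in the other two. Footnote 2 agrees in words: "Women of childbearing potential require a negative pregnancy test prior to starting treatment". The same footnote sets the contraception duty: "Patients of reproductive potential must use secure methods of contraception during treatment and for 3 additional months after the end of treatment".

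Section 4.2.1, an exclusion criterion, states: "Pregnancy tests must be obtained in girls who are post-menarchal". It gives no repeat interval. It also states: "Those who become pregnant while on treatment with entinostat must discontinue immediately and consult their treating physician". Section 10.1(h) makes pregnancy a reason for removal from protocol therapy, and 13.7.1 requires expedited reporting.

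Under section 5.2 a cycle may be repeated if the patient has at least stable disease and "has again met laboratory parameters as defined in the eligibility section". The pregnancy test is not named there.

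**The concern.** The protocol treats fetal exposure as a real hazard. Section 2.2.2 reports embryo-fetal toxicity in rats and rabbits, and 13.7.1 describes the exposure as possibly teratogenic. The on-treatment response (stop, remove, report) depends on someone knowing that the patient is pregnant. The only required test comes before the first dose. A site that follows 8.1 exactly runs no test afterwards, however many cycles the patient receives. Nothing in the schedule prompts a first test in a girl who was premenarchal at entry and later reaches menarche. At stake is fetal exposure to weekly dosing that lasts longer than it needs to.

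**Working it through.** The plan gives no figure to reproduce on this point. The check is a comparison of sections, followed by a count of doses and tests.

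**1. Is the blank cell genuine?** Yes. Other rows of the table keep their column positions: albumin is blank only during Cycle 1, and the patient diary is blank only pre-study. Footnote 2 independently ties the test to the start of treatment.

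**2. Does another section supply a repeat test?**

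| Section | What it covers | Repeat test? |
|---|---|---|
| 4.2.1 | Testing of post-menarchal girls, among the entry criteria | No interval stated; on-study menarche not mentioned |
| 4.0 and 8.1 | Laboratory values to recheck before first dosing: CBC, bilirubin, ALT, creatinine | Pregnancy test not listed |
| 5.2 | Eligibility laboratory parameters met again before each cycle | Pregnancy test not named |
| 8.1 table | Work before later cycles, including history, examination, CBC, electrolytes, creatinine, ALT, bilirubin, albumin | Cell blank |
| 10.1(h), 13.7 | Removal and reporting | Concern known pregnancies only |

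No section explicitly schedules one.

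**3. Doses per required test.** Section 5.1 gives doses on Days 1, 8, 15 and 22, so 4 per 28-day cycle. Section 8.2.1 uses 6 cycles or more to define long-term stable disease. This serves as an illustration, not a typical duration.

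- Scheduled doses: 6 × 4 = 24.
- Required tests now: 1 at baseline, 0 afterwards.
- Tests with a pre-cycle repeat: 1 + (6 − 1) = 6, so 5 are added.
- Scheduled doses between consecutive tests with the repeat: 24 / 6 = 4.

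Doses actually taken may be fewer. Treatment can be held for toxicity, and if a dose is missed and "more than 12 hours have passed since the scheduled dosing time, this dose will be skipped".

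**4. Spacing of repeat tests.** The table note reads: "Studies may be obtained within 72 hours prior to the start of the subsequent cycle". With 28-day cycles on time and a 3-day window, consecutive pre-cycle tests fall 28 − 3 = 25 to 28 + 3 = 31 days apart. Four scheduled doses lie between them.

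**5. Can the group at risk be sized?** No. Section 11.4 projects 13 + 2 = 15 females of 36 (41.7%). Pro rata, that is 22 × 15/36 = 9.2 of the 22 expected in 11.1. This counts females, not post-menarchal or sexually active patients, and rests on historical enrollment. The documents give no menarchal status and no pregnancy rate.

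**The case against.** The best defence is that the plan is coherent as written. It manages fetal risk by a baseline test, mandatory contraception, immediate discontinuation and expedited reporting, and none of these provisions contradicts another. A reader might infer an internal contradiction from the stopping rule without a test. The documents do not support that: stopping on pregnancy and testing only at baseline are compatible.

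A second argument is textual. Section 4.2.1 also governs conduct on study, and its testing sentence has no time limit. Section 5.2 points back to Section 4.0, which contains 4.2.1, so a repeat test might be implied. This reading weakens the menarche part most. But it is only implicit, and the 8.1 schedule leaves the cell blank. If the sponsor intends that reading, the same edit would make it clear.

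Third, history and examination take place weekly in Cycle 1 and before each later cycle. They can ask about missed periods and can identify menarche on study. This stands and lowers the risk. A reader might infer that pregnancy would be masked, because 9.1.8 lists nausea, vomiting and fatigue as likely drug effects. That is plausible but is inference: no section says these symptoms would be misattributed, and missed periods are not among the listed drug effects. The case for the test does not need it.

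Finally, the benefit is partial, since up to 4 scheduled doses can still fall between tests. That also stands.

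**Conclusion.** The gap is confirmed: one required test before treatment, none scheduled afterwards, and no explicit rule for menarche on study. It merits a cheap safety improvement; it is not an error in the design. No endpoint, DLT rule or escalation decision changes.

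The size can be stated only as doses per test: 24 scheduled doses on one test over 6 cycles, against 4 between tests with the fix. The 4-dose figure assumes cycles on schedule and counts from the time a pregnancy is detectable; a conception too recent to show at one visit would be found at the next.

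Three stronger readings should be resisted. The 5 years allowed in 5.1 is a ceiling, so 5 × 365.25 / 28, or about 65 cycles on one test, is not an expected course. The pro rata figure of about 9 females is not a number of patients at risk. And repeat testing shortens undetected exposure but does not prevent it; prevention rests on contraception.

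**What to change.** In the 8.1 table, mark the pregnancy test in the column for subsequent cycles. Add to footnote 2:

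> Repeat before each subsequent cycle (hCG on the pre-cycle blood draw, or urine) in patients who are post-menarchal at that time; confirm a positive result clinically before dosing or removal, interpreting it against baseline hCG in patients with hCG-secreting tumors.

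Tying the test to menarchal status at each visit covers girls who reach menarche on study. The last clause is needed because 4.1.4 provides for "patients with pineal tumors and elevations of CSF or serum tumor markers including alpha-fetoprotein or beta-HCG", in whom a raised hCG need not mean pregnancy.

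Cost: one hCG per cycle in post-menarchal patients (5 per patient over 6 cycles), including those who rely on abstinence; a quantitative baseline hCG in any patient with an hCG-secreting tumor; and occasional confirmatory work-up with a possible short dose delay. Serum hCG uses blood already drawn before the cycle and needs no new visit. Urine would need an extra sample, because urinalysis is scheduled only pre-study.

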8.2 Radiology Studies

8.2.1 Central Radiology Review for Response: Patients who respond (CR, PR) to therapy or have long term stable disease (SD) (≥ 6 cycles) on protocol therapy will be centrally reviewed. COG Operations Center will notify the Imaging Center of any patient requiring central review. The Imaging Center will then request that the treating institution forward the requested images for central review. The central image evaluation results will be entered into RAVE for review by the COG Operations Center and for data analysis.

The images are to be forwarded electronically to the Imaging Research Center at Children's Hospital Los Angeles via the ImageInBox. COG institutions that are not connected via the ImageInBox can send the images on CD ROM or USB flash drive. Submitted imaging studies should be clearly marked with the COG patient ID, study number (STUDY #ADVL1513) and date and shipped to [name] at the address below:

[name], CRP
Administrator, Imaging Research Center
Children's Hospital Los Angeles
[name]
[name]

8.3 **Pharmacology (required)**

8.3.1 Description of Studies and Assay

Pharmacokinetics (PK) will be performed to determine the PK of entinostat in children. Pharmacokinetic analysis will be conducted at a centralized laboratory using validated assays.

8.3.2 Sampling Schedule (See Appendix VI)

Blood samples will be obtained prior to drug administration and at the following time points:

- **Day 1 of Cycle 1:** pre-dose, and at 0.5, 1, 3, 6, 24 (Day 2), and 48 to 96 hours post-dose.
- **Day 8 of Cycle 1:** pre-dose.
- **Day 22 of Cycle 1:** pre-dose, 1 hour post-dose.
- **Day 28 of Cycle 1:** prior to Day 1, Cycle 2 dose.

8.3.3 Sample Collection and Handling Instructions

Blood samples (3 ml) will be collected in specified collection tubes according to the lab manual. Sample kits with pre-printed labels will be provided by Covance.

8.3.4 Sample Processing

Samples will be processed according to the lab manual.

8.3.5 Sample Labeling

Each tube must be labeled with the patient's COG patient ID number. If not using pre-printed labels, they must also be labeled with the date and time the sample was drawn. Data should be recorded on the Pharmacokinetic Study Form, which must accompany the samples. Sample kits with pre-printed labels will be provided by Covance.

8.3.6 Sample Shipping Instructions

Samples should be batched per patient and shipped frozen on dry ice in opaque containers at the end of Cycle 1 according to the lab manual.

8.4 Pharmacodynamic Studies (optional)

8.4.1 Description of Studies

In consenting patients, exploratory pharmacodynamic assessment of histone H3 and H4 acetylation will be performed in PBMCs to evaluate the change in acetylation after administration of entinostat as a potential biomarker of HDAC inhibition.

8.4.2 Sampling Schedule (See Appendix VII)

Whole blood specimens (3 ml) will be collected from all consenting patients at:

- **Day 1 of Cycle 1:** pre-dose, and at 6 and 24 (Day 2) hours post-dose.
- **Day 8 of Cycle 1:** pre-dose.

8.4.3 Sample Collection and Handling Instructions

Blood samples (3 ml) will be collected in CPT tubes for pharmacodynamic evaluation according to the lab manual. Record the exact time that the sample is drawn along with the exact time that the drug is administered. Sample kits with pre-printed labels will be provided by Covance.

8.4.4 Sample Processing

- Samples will be processed according to the lab manual.
- During blood draw, fill tube with blood as completely as possible. Mix the blood in the vacutainer tube by gently inverting the tube 6 to 8 times.
- Keep all samples refrigerated from the moment of drawing until shipment.

8.4.5 Sample Labeling

Each tube must be labeled with the patient's study registration number, the study I.D., and the date and time the sample was drawn. Data should be recorded on the Pharmacodynamics Study Form, which must accompany the sample(s). Sample kits with pre-printed labels will be provided by Covance.

8.4.6 Sample Shipping Instructions

- Keep all samples refrigerated from the moment of drawing until shipment.
- Samples must be shipped THE SAME DAY as blood is taken using overnight shipping. If possible, schedule of treatment should be planned to avoid sending samples on Fridays and Saturdays.
- Sample tubes should be placed in a plastic bag and preferably be packed with a cold pack (like U-tek -1°C/+30°F Tegrant Corporation cold pack) rather than a frozen ice pack. To minimize any movement during transit and prevent damage of blood cells, the plastic bag with tubes must be properly insulated from the cold pack with packing material (bubble wrap, paper towels, crumpled paper, etc.) and placed on the cold pack (not

THIS PROTOCOL IS FOR RESEARCH PURPOSES ONLY, SEE PAGE 1 FOR USAGE POLICY

between bottom of the box and pack or between 2 cold packs) so that tubes do not touch the pack. Please avoid using wet ice, as accidental contact with water will break down blood cells. Please also fill any empty space in the package with packing material.

- Refer to instructions in the lab manual.
- Include [Appendix VII](#), Pharmacodynamic Study Form, with the shipment
- Ship samples to the following address:

[name] Laboratory
CCR, NCI, NIH
[name]
[name]
[name]

